### 5.2. Data Sets Analysed and protocol deviations

#### Data sets analysed

There will be two subject sets defined for this study: All Included Set (AIS) and Treated Set (TS).

All Included Set (AIS): this is the target set consisting of all subjects enrolled in the study and having signed the informed consent. This set will be used for describing disposition, demographic data, medical history and concomitant medication, unless otherwise noted.

Treated Set (TS): will include all AIS subjects receiving at least one injection of the mixture of Lipiodol® Ultra Fluid and surgical glues regardless of the quantity. This set will be used for describing demographic and baseline data, extent of exposure and all safety and efficacy parameters.

Analyses Sets	AIS	TS
Disposition	✓	
Demographics and Baseline characteristics	✓*	✓
Exposure		✓
Safety assessment: Main criterion		✓
Safety assessment: Secondary criteria		✓
Efficacy assessment		✓
Long term follow-up assessment		✓
Listings	✓	

\* If there is a difference higher than 10% between the number of patients in AIS and in TS.

#### Protocol deviations

As per ICH E3 guideline, a protocol deviation is any change, divergence, or departure from the study design or procedures defined in the protocol, with or without impact to the patient safety or the efficacy assessments. Protocol deviations are displayed in the Clinical Study Report (CSR) as a metric of the feasibility and reliability of the study. The list of protocol deviations is presented in the table below and can be updated if necessary. Protocol deviations will be gathered from monitoring files and clinical database.

Of note, if the reason of deviations is related to the COVID pandemic then it will be indicated in the Statistical Data Review Meeting Minutes (DRM) and the corresponding deviation presented apart.

The deviations are listed in the table below:

Category	Description	Source
Inclusion criteria not met/	Inclusion criteria n°01 not met	Clinical data base
Non-inclusion criteria met	Inclusion criteria n°02 not met	Monitoring
	Inclusion criteria n°03 not met	Clinical data base
	Inclusion criteria n°04 not met	Monitoring
	Inclusion criteria n°05 not met	Clinical data base
	Non-inclusion criteria n°01 met	Monitoring
	Non-inclusion criteria n°02 met	Clinical data base
	Non-inclusion criteria n°03 met	Monitoring
	Non-inclusion criteria n°04 met	Monitoring
	Non-inclusion criteria n°05 met	Monitoring
	Non-inclusion criteria n°06 met	Clinical data base
	Non-inclusion criteria n°07 met	Clinical data base
	Non-inclusion criteria n°08 met	Clinical data base
	Non-inclusion criteria n°09 met	Monitoring
	Non-inclusion criteria n°10 met	Monitoring
	Non-inclusion criteria n°11 met	Monitoring
	Non-inclusion criteria n°12 met	Monitoring
	Non-inclusion criteria n°13 met	Monitoring

Category	Description	Source
Forbidden concomitant medication	Concomitant medication significantly impacting safety (Beta-blockers, Metformin, Interleukin II)	Clinical data base
	Concomitant medication with effective anti-coagulant therapy	Clinical data base
IMP deviation	Temperature excursion for IMP	Monitoring
	IMP management not appropriate	Monitoring
	Volume of Lipiodol® Ultra Fluid > 15 mL	Clinical data base
	Lipiodol and surgical glue mixture not administered via selective arterial catheterization	Monitoring
Missing data	Age is missing	Clinical data base
	Sex is missing	Clinical data base
	Weight is missing	Clinical data base
	Height is missing	Clinical data base
	Medical history is missing	Clinical data base
	Number of lesions to be treated is missing	Clinical data base
	Location of lesions to be treated is missing	Clinical data base
	Type of lesions to be treated is missing	Clinical data base
	Target level obliteration is missing	Clinical data base
	Name of associated surgical glue is missing	Clinical data base
	Volume of mixture used is missing	Clinical data base
	Mixture ratio is missing	Clinical data base
	Post-procedure obliteration obtained is missing	Clinical data base
	Other embolization material used is missing	Clinical data base
Non-respect of study's schedule and procedures	Enrolment visit (ICF signature date) performed more than 7 days before study procedure	Clinical data base
	Optional Second study procedure performed more than 30 days after first study procedure	Clinical data base
	Follow-up visit performed less than 27 days or more than 33 days after last study procedure	Clinical data base
	Compatibility between Lipiodol and glue not performed by site	Monitoring
GCP deviation	Deviations related to ICF signature process	Monitoring
	Source document management not appropriate	Monitoring
	SAE Management not appropriate	Monitoring

Frequency and percentages of subjects with protocol deviations will be presented. A listing of all protocol deviations will also be provided in CSR appendix 16.2.2.

### 5.3. Measurements of study drug compliance

Study drug in this study refers to the mixture. No analyses will be performed on study drug compliance.

### 5.4. Demographic and Other Baseline Characteristics

Demographic and Other Baseline Characteristics will be tabulated using the AIS and TS.

CONFIDENTIAL	STATISTICAL ANALYSIS PLAN N° LUF-44-001  VERSION N° 2.0	Page 15 / 29
--------------	---	--------------

#### **5.4.1. Demographic data**

The following demographic parameters, at enrolment (Day -7 to Day 0), will be presented:

- Age (in years),
- Gender,
- Body weight (in kg),
- Height (in cm),
- BMI (in kg/m^2).

Summary statistics (number [n], mean, standard deviation [SD], median, minimum, and maximum) will be calculated for age, body weight, height and BMI. Frequency and percentages will be calculated for gender. The denominator will be the number of subjects in the set for which demographic characteristics summaries will be presented.

Listing of all demographic parameters will be presented in CSR Appendix 16.2.4.

#### **5.4.2. Study disease**

Summary statistics (number [n], mean, standard deviation [SD], median, minimum, and maximum) will be calculated for the number of lesions to be treated with the mixture. Number and frequency of the variable "number of lesions to be treated" categorized in class will be also tabulated (1 lesion, 2 lesions, 3 lesions and > 3 lesions).

The main lesions (up to three) to be treated with the mixture will be described in terms of location and type. Summary tables will present these characteristics by subject (number and % of subjects) and by lesion (number and % of lesions).

#### **5.4.3. Risk factors**

Not Applicable.

#### **5.4.4. Medical history and concomitant diseases**

Medical History and associated diseases will be coded in System Organ Class (SOC) and Preferred term (PT) using the Medical Dictionary for Regulatory Activities (MedDRA) latest version in force at the date of data base lock.

Summary tables (number and % of subjects) grouped by SOC and PT will be presented for Medical History firstly (past) then for concomitant diseases (present). Medical histories are those "Not Ongoing" and concomitant diseases are those "Ongoing" at the enrolment visit. The number and % of subjects presenting with at least one Medical History under medication will be presented.

Listing of all diseases, with a flag for ongoing diseases, will be presented in CSR Appendix 16.2.4.

#### **5.4.5. Clinical laboratory evaluation at baseline**

Not Applicable.

#### **5.4.6. Vital signs, physical findings and other observations related to safety at baseline**

Not Applicable.

CONFIDENTIAL	STATISTICAL ANALYSIS PLAN N° LUF-44-001  VERSION N° 2.0	Page 16 / 29
	DATED: JUNE 30, 2021	

#### 5.4.7. Prior therapies

Subjects' prior medications within 7 days prior to the first study procedure will be coded in Anatomic Therapeutic Chemical (ATC) using the WHO Drug dictionary latest version in force at the date of data base lock.

Summary tables (number and % of subjects) grouped by the first and the last level of ATC codes will be presented for prior medications (those with "End of Treatment" coded 1, 2 or 3).

Listing of all prior medications will be presented in CSR Appendix 16.2.4.

#### 5.4.8. Other baseline characteristics

##### 5.4.8.1 Therapeutic/Palliative strategy at enrolment

Summary tables will present the number of subjects with at least one previous procedure and one next scheduled procedure, together with the type of procedure (number and % of subjects). Previous and next type of procedure will also be presented by lesion (number and % of lesions).

##### 5.4.8.2 Second vascular embolization at enrolment

A summary table will display the number of subjects with at least one second procedure using the mixture scheduled within the next 30 days, (number and % of subjects).

Listing of all other baseline characteristics will be presented in CSR Appendix 16.2.4.

### 5.5. Efficacy evaluation

All efficacy analysis will be conducted using the TS. Descriptive statistics will be summarized per lesion and per procedure (if applicable) on all available efficacy data.

The following parameters will be presented:

- Number and frequency of the target obliteration scores defined before any procedure,
- Number and frequency of the post-procedure obliteration scores (including for the lesions not targeted initially),
- Number and frequency of lesions embolization.

These analyses will be repeated according to the surgical glue (Histoacryl®, Endoacryl®, Other) associated to Lipiodol® Ultra Fluid.

In case of second procedure, the following analyses will be presented:

- Summary statistics (number [n], mean, standard deviation [SD], median, minimum, and maximum) will be calculated for the number of lesions to be treated with the mixture,
- Number and frequency of the variable "number of lesions to be treated" categorized in class will be also tabulated (1 lesion, 2 lesions, 3 lesions and > 3 lesions),
- The main (up to three) and new lesions to be treated with the mixture will be described in terms of location and type, separately. Summary tables (number and % of subjects) will be tabulated. Description will be also presented by lesion (number and % of lesions).

Listings of all efficacy data will be presented in CSR appendix 16.2.6.

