Study product: Lipiodol® Ultra Fluid (480 mg I/ml), solution for injection	Active Ingredient(s): Ethyl esters of iodized fatty acids of poppy seed oil (Lipiodol® Ultra Fluid)	
with study documents, even if it is obvious that more data will be needed in order to draw any conclusion.		
The Investigator and Guerbet shall forward their reports after due analysis, to the Chairman of the Ethics Committee, Licensing Authority (DCGI office) and Head of Institution where the trial has been conducted within 14 calendar days of occurrence of the serious adverse event.		
Statistical methods		
Descriptive statistical methods will be used to report all safety and efficacy assessments.		
For assessment of the safety, occurrence of ADRs and AEs will be tabulated in terms of number and percentage as well as their associated characteristics such as intensity, actions taken, outcome, causal relationship to the mixture of Lipiodol® Ultra Fluid associated with surgical glues and causal relationship to the study procedure of vascular embolization.		
The efficacy of the procedure will be described in terms of number and frequency of obliteration (target and post-procedure) scores and in terms of number and frequency of lesions embolizations matching target.		

 CONFIDENTIAL	Protocol No. LUF-44-001 Version No. 3.0 Date January 20 th 2017	Page 6 / 43
---	--	-------------

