## 4 SUBJECT SELECTION

### 4.1 Inclusion Criteria

To be included in the study, the subject must meet all the following inclusion criteria:

1. Female or male adult subject older than 18 years
2. Subject presenting with vascular lesions/anomalies whether malformative (arterial, venous, arteriovenous, fistula) or tumoral (benign: hemoangioma; malignant, angiosarcoma) eligible for vascular embolization of single or multiple lesion(s), using selective transarterial catheterization and Lipiodol® Ultra Fluid in association with surgical glues as only embolization material, in the next stage of the therapeutic or palliative strategy
3. Subject not previously treated for this/those lesion(s) by vascular embolization using Lipiodol® Ultra Fluid in association with surgical glues
4. Subject able and willing to participate to the study
5. Subject having read the information, having consented to audio-visual recording of informed consent process and having provided his/her consent to participate in writing by dating and signing the informed consent form or subject unable to consent in writing whose free and voluntary consent is confirmed in writing by a legal representative or impartial witness, prior to any study related procedure being conducted (as described in section 13.3)

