### 4.2 Non Inclusion Criteria

Subjects presenting with one or more of the following non-inclusion criteria must not be included in the study:

1. Subject scheduled for vascular embolization using embolization materials and radiopaque material other than Lipiodol® Ultra Fluid in association with surgical glues (e.g. embolizing fluids such as alcohol or sclerosant agents; particles; implants such as coils or microcoils or balloons; powdered metals such as tantalum or tungsten), whether in combination or alone
2. Subject with known contra-indications to vascular embolization (e.g. severe coagulation disorder, infectious syndrome)
3. Subject for whom lesion(s) to be embolized is/are acutely bleeding
4. Subject presenting life-threatening emergency situation
5. Subject with known contra-indication(s) to the use or with known sensitivity to Lipiodol® Ultra Fluid, to its ingredients or to drugs from a similar pharmaceutical class
6. Subject currently treated with beta-blockers, metformin or subject who stopped beta-blockers, metformin less than 2 days prior to vascular embolization as described in Lipiodol® Ultra Fluid Summary of Product Characteristics
7. Subject previously treated with Interleukin II as described in Lipiodol® Ultra Fluid Summary of Product Characteristics
8. Subject currently treated with effective anticoagulant therapy
9. Pregnant or breast-feeding female subject
10. Subject having received any investigational medicinal product within 7 days prior to enrolment

Guerbet    CONFIDENTIAL	Protocol No. LUF-44-001 Version No. 3.0 Date January 20 th 2017	Page 18 / 43
--	--	--------------

11. Subject with anticipated, current or past condition (medical, psychological, social or geographical) that would compromise the subject's safety or her/his ability to participate to the study
12. Subject unlikely to comply with the protocol, e.g. uncooperative attitude, and unlikely to complete the study
13. Subject related to the Investigator or any other study staff or relative directly involved in the study conduct

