### 9.2 First Study procedure

The study procedure is a vascular embolization using Lipiodol® Ultra Fluid in association with surgical glue (the mixture) via selective arterial catheterization.

Site staff will collect the following information related to the first study procedure:

- The conditions of mixture administration: date of the procedure, time of first injection of the mixture, associated surgical glue (brand name), puncture site, time leaving the catheterization laboratory, number of injections, and per injection : concerned lesion, ID number of IMP, mixture ratio of Lipiodol® Ultra Fluid to surgical glue, total volume, catheter flush if any (yes/no)
- Changes in therapeutic/palliative strategy introducing additional embolization material
- Post-procedure obliteration (evaluated according to 4 level-score: 1. <50%; 2. 50-75%; 3. 75-99%; and 4. 100% corresponding to a complete nidus obliteration rate) per lesion assessed on

 CONFIDENTIAL	Protocol No. LUF-44-001 Version No. 3.0 Date January 20 th 2017	Page 25 / 43
---	--	--------------

earliest available angiogram after the first embolization procedure (e.g. DSA, CTA, MRA, US, Doppler US)

- Safety information: adverse event(s), whether serious or not. For more information on safety reporting, refer to Section 10
- Concomitant medications

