### 1.1. Study objectives

The primary objective is to evaluate the per-procedure safety of Lipiodol® Ultra Fluid in association with surgical glues during vascular embolization.

The secondary objectives of the trial are:

- to evaluate the safety of Lipiodol® Ultra Fluid in association with surgical glues up to one month after the last vascular embolization procedure,
- to evaluate the efficacy of Lipiodol® Ultra Fluid in association with surgical glues in vascular embolization.

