### 2.2. Efficacy criteria

Efficacy criteria are the following assessments:

- Target obliteration per lesion evaluated before the first procedure according to 4 level-score: 1. <50%; 2. 50-75%; 3. 75-99%; and 4. 100% corresponding to a complete nidus obliteration rate,
- Post-procedure obliteration per lesion evaluated after each procedure according to the same 4 level-obliteration-score,
- Successful lesions embolization expressed as the lesions achieving the targeted percentage of obliteration.

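### The visible text of SAP 5.5 gives no summary of target achievement with the mixture alone, separate from lesions given added embolic material

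*SAP*

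**What the plan says.** **Objective and eligibility.** The second secondary objective in SAP 1.1 is "to evaluate the efficacy of Lipiodol® Ultra Fluid in association with surgical glues in vascular embolization". Protocol 4.1 (criterion 2) requires "Lipiodol® Ultra Fluid in association with surgical glues as only embolization material", and Protocol 4.2 (criterion 1) bars a "Subject scheduled for vascular embolization using embolization materials and radiopaque material other than Lipiodol® Ultra Fluid in association with surgical glues". Both rules concern what is planned.

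**Additions during the procedure.** Protocol 9.2 has the site record "Changes in therapeutic/palliative strategy introducing additional embolization material". Protocol 9.3 repeats the item for the optional second procedure.

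**Success.** SAP 2.2 defines it as "Successful lesions embolization expressed as the lesions achieving the targeted percentage of obliteration". It sets no condition on the material used.

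**Analysis.** SAP 5.5 works on the Treated Set, which SAP 5.2 opens to any subject with at least one injection of the mixture in any quantity. On data: "Descriptive statistics will be summarized per lesion and per procedure (if applicable) on all available efficacy data". On breakdowns: "These analyses will be repeated according to the surgical glue". SAP 3.11 gives subgroups as not applicable.

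**Where added material appears.** SAP 5.6.1 tabulates its use and type per subject, procedure and lesion, as exposure. The deviation list in SAP 5.2 mentions it only as an item that may be missing.

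**A wording gap in the same section.** Protocol 12.4 promises the number of lesions whose embolization matches the target. The third bullet of SAP 5.5 drops the reference to the target.

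**The concern.** The objective and the entry criteria describe one treatment: the mixture used alone. The efficacy tables describe a slightly different one: the mixture plus whatever else the operator added. Post-procedure obliteration is read on the earliest available angiogram after the procedure, so for a lesion that also received other material the score reflects everything used. If such a lesion reaches its target, it counts as a success under an objective that names only the mixture.

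The exposure table will show how often other material was used. No visible summary table crosses this with obliteration or target achievement. A reader who wants the success rate of the mixture alone would have to rebuild it from the exposure and efficacy listings. What is at stake is how a secondary descriptive rate is read. The primary safety criterion and the sample size are not affected.

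**Working it through.** The plan has no figure to reproduce. The sample size of 125 is a regulatory requirement, and the documents state neither an expected success rate nor an expected share of lesions with added material. The arithmetic below only shows what the planned tables can and cannot determine. Its inputs are assumptions.

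**Notation.**
- m = share of lesions given added material (assumed 5%, 10% and 20%; it may be near zero, since scheduled use is excluded)
- s = success rate in mixture-only lesions
- a = success rate in lesions with added material
- R = all-lesion success rate = (1 − m)s + m·a (assumed 80%)
- C = proportion of all lesions that reached target without added material = (1 − m)s

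**Two comparisons.**
- R − C = m·a. This is never negative and is at most m.
- R − s = m(a − s). This can have either sign.

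**What R and m alone determine.** C lies between R − m and the smaller of R and 1 − m. Dividing by 1 − m gives the range for s. With R = 80%:

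| m | Range of C | Range of s |
|---|---|---|
| 5% | 75% to 80% | 0.75/0.95 = 78.9% to 0.80/0.95 = 84.2% |
| 10% | 70% to 80% | 0.70/0.90 = 77.8% to 0.80/0.90 = 88.9% |
| 20% | 60% to 80% | 0.60/0.80 = 75% to 0.80/0.80 = 100% |

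The ends of each range are the extremes in which lesions with added material all succeed or all fail. The ranges also need m and R to share one denominator, and the SAP does not guarantee this. SAP 3.1 bases percentages on non-missing records, and the obliteration scores in SAP 5.5 include lesions not targeted initially.

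**Direction, at m = 10%.**
- s = 75%, a = 95%: R = 0.675 + 0.095 = 77%, which is 2 points above s. C = 67.5%.
- s = 80%, a = 50%: R = 0.72 + 0.05 = 77%, which is 3 points below s. C = 72%.

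The same all-lesion rate of 77% thus arises from two different results for the mixture. The exposure table, which gives only m, cannot tell them apart.

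**Size of the added-material group.** Assuming 125 lesions and m = 10%, there would be about 12 such lesions. An observed 10/12 has an exact 95% interval of 51.6% to 97.9%.

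**The case against.** The strongest reply is that nothing was promised and little is hidden. Protocol 12.4 specifies all available efficacy data, per lesion, on the treated set, and SAP 5.5 follows it on this point. The protocol synopsis states: "The efficacy of the procedure will be described in terms of number and frequency of obliteration". On that reading the all-lesion rate is the intended quantity. Planned use of other material is excluded, unplanned use is tabulated under exposure, and both listings will exist. If additions prove rare, the question closes. The illustrated shifts of 2 or 3 points are also small beside sampling error: 100/125 has an exact 95% interval of 71.9% to 86.6%.

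Much of this stands. The all-lesion rate should stay, the effect may be negligible, and the study tests no hypothesis. What remains is that the objective names the mixture, the entry criteria define it as the only material, and no visible table reports that quantity although the data are held per lesion.

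A reader might infer three stronger things that the documents do not support:
- **That pooling inflates the efficacy of the mixture.** Against the mixture-only lesions, the pooled rate may be higher or lower.
- **That the whole SAP lacks this split.** Sections 4 and 6 cannot be seen, so only the visible text can be judged.
- **That a mixture-only stratum would give an unbiased answer.** Other material is added by a decision made during the procedure, perhaps because the mixture was not reaching the target. Selecting lesions on that decision may flatter the mixture.

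**Conclusion.** The point holds in a limited form. In the visible SAP text, target achievement is summarized over all treated lesions, with or without added material, and repeated only by glue brand. No visible summary table shows how often the target was reached with the mixture alone.

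The size and direction are unknown. The 5% to 20% shares, the 80% success rate and the 125 lesions are assumptions, and the ranges need a common denominator that the plan does not secure. The consequence is confined to the reading of a secondary, untested criterion. The change is worth making because it is cheap and supplies a quantity that the planned tables cannot give. The missing reference to the target in the third bullet of SAP 5.5 is a separate wording mismatch. It needs correcting whatever the share of added material.

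**What to change.** In SAP 5.5, keep the all-lesion rate and add the following.

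1. **Main addition.** Report the proportion of treated lesions with a pre-set target that reached it with no other material recorded as used, on the same denominator as the all-lesion rate. Lesions with added material, or with material not recorded, count as not reaching target by the mixture alone. The figure is then a true lower bound for mixture-alone success and should be labelled so.
2. **Counts.** For each procedure, tabulate target achievement by added material (yes / no / not recorded), using the material recorded for that lesion at that procedure and the target set for that procedure. For summaries across procedures, class a lesion as mixture-only only if 'no' is recorded at every study procedure.
3. **Caveat.** State that the mixture-only stratum is defined by a decision made during the procedure, may flatter the mixture, and is descriptive only.
4. **Separate correction.** Restore the reference to matching the target in the third bullet, so that it agrees with Protocol 12.4 and SAP 2.2.

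The cost is SAP wording, one small table and one proportion, with no new data collection. The added-material group will probably be too small to read as more than counts.
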